10.1.5 Causality of AEs

The relationship of each AE to study medication(s) will be assessed using the following categories:

- Related: An AE that follows a reasonable temporal sequence from administration of a drug (including the course after withdrawal of the drug), or for which possible involvement of the drug can be argued, although factors other than the drug, such as underlying diseases, complications, concomitant drugs and concurrent treatments, may also be responsible.
Not Related: An AE that does not follow a reasonable temporal sequence from administration of a drug and/or that can reasonably be explained by other factors, such as underlying diseases, complications, concomitant drugs and concurrent treatments.

10.1.6 Relationship to Study Procedures

Relationship (causality) to study procedures should be determined for all AEs.

The relationship should be assessed as Related if the investigator considers that there is reasonable possibility that an event is due to a study procedure. Otherwise, the relationship should be assessed as Not Related.

10.1.7 Start Date

The start date of the AE is the date that the first signs/symptoms were noted by the subject and/or physician.

10.1.8 Stop Date

The stop date of the AE is the date at which the subject recovered, the event resolved but with sequelae or the subject died.

10.1.9 Action Concerning Study Medication

- Drug withdrawn – a study medication is stopped due to the particular AE.
- Dose not changed – the particular AE did not require stopping a study medication.
- Unknown – only to be used if it has not been possible to determine what action has been taken.
- Not Applicable – a study medication was stopped for a reason other than the particular AE eg, the study has been terminated, the subject died, dosing with study medication was already stopped before the onset of the AE.
- Dose Interrupted – the dose was interrupted due to the particular AE.

10.1.10 Outcome

- Recovered/Resolved – Subject returned to first assessment status with respect to the AE.
- Recovering/Resolving – the intensity is lowered by one or more stages: the diagnosis or signs/symptoms has almost disappeared; the abnormal laboratory value improved, but has not returned to the normal range or to baseline; the subject died from a cause other than the particular AE with the condition remaining “recovering/resolving”.
- Not recovered/not resolved – there is no change in the diagnosis, signs or symptoms; the intensity of the diagnosis, signs/ symptoms or laboratory value on the last day of the observed study period has got worse than when it started; is an irreversible congenital anomaly; the subject died from another cause with the particular AE state remaining “Not recovered/not resolved”.
- Resolved with sequelae – the subject recovered from an acute AE but was left with permanent/significant impairment (eg, recovered from a cardiovascular accident but with some persisting paresis).
- Fatal – the AEs which are considered as the cause of death.

- Unknown – the course of the AE cannot be followed up due to hospital change or residence change at the end of the subject’s participation in the study.

10.2 Procedures

10.2.1 Collection and Reporting of AEs

10.2.1.1 AE Collection Period

Collection of AEs will commence from the time that the subject signs the informed consent to participate in the study continue until V7.

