6.0 STUDY DESIGN AND DESCRIPTION

6.1 Study Design

The total duration of this randomized, multicentre, phase III trial is 24 weeks maximum. It includes six weeks of single-blind placebo administration during the run-in period and 16 weeks of double-blind treatment, followed by a single safety visit (within two weeks) for subjects undergoing the second (final) bronchial biopsy.

This trial will be performed in Chronic Obstructive Pulmonary Disease (COPD) patients (GOLD stage II-III, **in Germany stage II only**) and will include two parallel treatment arms (placebo and Roflumilast 500 µg once daily). A 1:1 randomization scheme will be used, i.e. Subjects will be allocated to Roflumilast 500 µg or placebo in equal proportions. Randomization will be stratified by concomitant LABA use.

[figure not shown]
The trial consists of the following periods:

- **Single-blind placebo run-in period** (6 weeks) with visits scheduled at weeks: -6 (V0), -2 (V1) and 0 (V2, randomization visit).
- **Double-blind treatment period** (16 weeks) with visits scheduled at 6, 14, and 16 weeks of treatment (V4-V6). An additional visit V3 will have to be performed within two weeks after bronchoscopy/bronchial biopsy purely as a safety visit. The exact timing of this safety visit will be determined by the Investigator.
- **Safety follow-up.** All adverse events (AEs) will be followed up to 30 days after the double-blind treatment period has been completed. An additional safety visit V7 will be scheduled within 2 weeks after the second bronchoscopy. The exact timing of the safety visit will be determined by the Investigator.

A schematic of the study design is included as [Figure 6.a](#). A schedule of assessments is listed in [Appendix A](#).

Figure 6.a Schematic of Study Design

Single-blind run-in: 6 weeks	Double-blind treatment including Safety follow-up V3 for Subjects undergoing bronchoscopy 16 weeks	Safety follow-up including V7 for Subjects undergoing the second bronchoscopy 2 weeks
---------------------------------	---	--

Therapy consisting of any bronchodilator (SABA, SAMA, LABA, LAMA) or their combination in stable doses. Rescue medication: SABA or SAMA

Abbreviations: V2 – randomization visit and first bronchoscopy, V6 – visit at the end of double blind treatment period and second bronchoscopy, LABA – Long-Acting β_2 -Agonist, LAMA – Long-Acting Muscarinic Antagonist, SABA – Short-Acting β_2 -Agonist, SAMA – Short-Acting Muscarinic Antagonist, o.d. – once daily

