9.3.6 Follow-up / Visit V7 (≤ 2 weeks after visit V6)

For all randomized Subjects who completed the trial as scheduled and the final bronchial biopsy was performed at V6, a follow-up visit (V7) will be performed within two weeks after V6 to receive information about the Subject's well being after the bronchoscopy.

The following assessments or procedures will be performed:

- Concomitant medications (see Sections 7.6, 7.7, 9.1.7)
- Physical examination (see Section 9.1.3)
- Vital signs (e.g. heart rate, blood pressure) and body measurements (body weight and height) (see Sections 9.1.4, 9.1.5)
- Adverse event assessment

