10.2.2 Collection and Reporting of SAEs

When an SAE occurs through the AE collection period it should be reported according to the following procedure:

A Takeda SAE form must be completed, in English, and signed by the investigator immediately or within 24 hours of first onset or notification of the event. The information should be completed as fully as possible but contain, at a minimum:

- A short description of the event and the reason why the event is categorized as serious.
- Subject identification number.
- Investigator's name.
- Name of the study medication(s)
- Causality assessment.

The SAE form should be transmitted within 24 hours to the attention of the contact listed in Section 1.1.

Any SAE spontaneously reported to the investigator following the routine AE collection period should be reported to the sponsor if considered related to study participation.

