13.1.1.4 Valid Cases Set

The valid cases set (VCS) consists of all Subjects of the FAS without any major protocol violations. Subjects terminating prematurely will be included in the VCS provided that there is no major protocol violation.

Subjects with major protocol violations considering the inclusion criteria, randomization criteria, and criteria affecting the read-out parameters of the trial will be identified during review of the blinded data. Violation of the criteria within ethical considerations in terms of general health are considered minor deviations in terms of impact on interpretability of the data, but it will be assessed during review of the blinded data if there is an impact for single cases. Deviations occurring during the following procedures will not be considered major protocol violations for the primary objective of the trial: Telephone contacts after early withdrawal and follow-up visit after regular trial end.

The Per-Protocol (PP) analysis is based on the VCS. In analogy to the ITT analysis it will be performed on an 'as randomized' basis.

The PP analysis will be used to assess the robustness of the results and will be performed for the primary and key secondary endpoints (see Section 13.1.3.2) only.

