- *For visits where subjects will not undergo blood draws or biopsies, the fasting requirement will only be mandated if clinically indicated as per investigator judgement.

Abbreviations:

R - Randomization (V2); V0 - visit 0, VE - visit end (V6), FU safety visit - follow-up safety visit (V7)

^{a)} Applies only to Subjects, who underwent the second bronchoscopy/bronchial biopsy at V6.

^{b)} Time windows for the run-in period always refer to V0, whereas those for the treatment period always refer to the randomization visit V2.

^{c)} Body height measurement only at visit V0.

^{d)} If confirmation or check of V0 laboratory values is necessary. Pregnancy test is optional.

^{e)} For female Subjects of childbearing potential or less than 1 year postmenopausal.

^{f)} If not performed within past three months. Examination results must be available.

GERMANY ONLY: Every patient should have a historical X-ray or CT scan available to clarify the exclusion criteria #18.

^{g)} This should be done prior to pulmonary function test.

^{h)} Tablet compliance calculation by the investigational site (see Section 9.2) to check for randomization criterion no. 2 (see Section 7.3).

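### AE collection and full SAE reporting end at V7, which is not scheduled for subjects without the second biopsy and falls short of the 30 days stated in Section 6.1

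*Protocol*

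**What the plan says.** All references are to the protocol.

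- **End of AE collection.** Section 10.2.1.1: "Collection of AEs will commence from the time that the subject signs the informed consent to participate in the study continue until V7". No other end point is given.
- **SAEs.** Section 10.2.2 uses the same period: "When an SAE occurs through the AE collection period it should be reported according to the following procedure". Beyond it, only SAEs that reach the investigator spontaneously are covered; those arising "following the routine AE collection period should be reported to the sponsor if considered related to study participation".
- **Who has V7.** Appendix A, footnote a: "Applies only to Subjects, who underwent the second bronchoscopy/bronchial biopsy at V6". Section 9.3.6 adds a second condition, that the subject completed as scheduled, and places V7 within two weeks of V6. Section 6.1 leaves the exact day to the investigator.
- **The other time frame.** Section 6.1, repeated in the synopsis: "All adverse events (AEs) will be followed up to 30 days after the double-blind treatment period has been completed".
- **Early termination.** Section 7.8 asks that a subject who stops early be called in for a last visit if possible. Section 9.3.5 prescribes the V6 assessments, with bronchoscopy only if the subject agrees. Those assessments include AEs. Neither section schedules a later contact.
- **Telephone contact.** Section 13.1.1.4 names, among procedures in which deviations are not major violations, "Telephone contacts after early withdrawal and follow-up visit after regular trial end". No section and no row of Appendix A schedules such a call.
- **Events already known.** Section 10.2.1.2 keeps every subject with an AE under monitoring until symptoms subside or are explained. New events found during that monitoring are reportable.

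**The concern.** A collection period has to close on a date that exists for every treated subject. Here it closes on a visit whose existence depends on whether the subject completed and was biopsied a second time. For everyone else the text does not say when solicited AE collection stops, nor when SAE reporting changes from all SAEs to only related ones reported spontaneously.

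Among subjects who do have V7, the close varies with the day the investigator picks and cannot reach the 30 days of Section 6.1.

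What is at stake is the safety data, not the primary endpoint. Sites following the written rule will look for new events over different lengths of time according to completion and biopsy status. A new AE, or an SAE not considered related, that arises after a termination visit in a subject with nothing ongoing has no scheduled route into the database. Events that were never asked about cannot be recovered reliably at the analysis stage.

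**Working it through.** **Inputs.** 150 subjects randomized 1:1 (synopsis); 30% drop-out, called conservative, and 105 subjects with two bronchoscopies (Section 13.3); randomized and completed numbers for five cited trials (Section 13.3 table); V7 at most 14 days after V6 (Section 9.3.6); 30 days (Section 6.1); 6 weeks run-in, 16 weeks treatment, 24 weeks maximum (Section 6.1).

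**Step 1: the plan's own figure.** 150 × (1 − 0.30) = 105, as stated. Subjects without a second bronchoscopy, and so without V7 under footnote a: 150 − 105 = 45, or 30%.

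**Step 2: the same count at the cited trials' drop-out.** Drop-out = 1 − completed/randomized; subjects without V7 = 150 × drop-out.

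| Protocol reference | Randomized | Completed | Drop-out | Without V7, of 150 |
|---|---|---|---|---|
| 26 | 60 | 51 | 15.0% | 22.5 |
| 11 | 114 | 90 | 21.1% | 31.6 |
| 21 | 59 | 53 | 10.2% | 15.3 |
| 27 | 37 | 31 | 16.2% | 24.3 |
| 14 | 140 | 114 | 18.6% | 27.9 |

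The range is about 15 to 32 subjects.

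**Step 3: the two time frames.** Among subjects with V7, collection closes no later than 14 days after V6. Against 30 days this is short by at least 30 − 14 = 16 days.

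**Step 4: total duration.** With V7: 6 + 16 + 2 = 24 weeks, which equals the stated maximum. With 30 days: 6 + 16 + 30/7 = 26.3 weeks, which exceeds it. So the 24-week figure agrees with a V7 close and not with 30 days.

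**Step 5: what the text gives each type of subject.**

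| Subject | Is V7 scheduled? | End of collection |
|---|---|---|
| Completed as scheduled, second biopsy done | Yes | V7, at most 14 days after V6 |
| Completed, no second biopsy | No | Not defined |
| Stopped early, no bronchoscopy | No | Not defined |
| Stopped early, agreed to bronchoscopy | Unclear | Depends on which section is followed |

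The last row is a further inconsistency. Section 9.1.15 requires a safety visit within two weeks after each bronchoscopy, and footnote a can be read to include this subject. Section 9.3.6 excludes anyone who did not complete as scheduled.

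**The case against.** The best defence is that Sections 6.1 and 10.2.1.1 concern different activities. Following known events for 30 days and soliciting new ones until V7 could both be true. The wording permits this, but the protocol never draws the distinction, and on this reading subjects without V7 still have no end of solicitation.

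The second defence is stronger. Section 10.2.1.2 applies to all subjects with an AE, whether or not they completed and whether or not the event is related. A subject who leaves because of an unresolved AE stays under observation, and new events found there are reportable. Section 10.3 follows SAEs to resolution. This stands, and it narrows the gap to new AEs and SAEs in subjects with no ongoing follow-up.

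Third, capture after withdrawal was foreseen: Section 13.1.1.4 mentions telephone contacts, and Section 13.1.3 allows for data obtained after discontinuation. That shows intent, but nothing schedules the contact.

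Finally, AE analysis details may be left to the SAP (Section 13.1.5.1). That is fair for analysis definitions. It does not settle the collection period, which the protocol itself fixes.

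**Conclusion.** The point holds and should be corrected. The stated end of AE collection and of full SAE reporting does not exist for 45 of 150 subjects at the protocol's conservative drop-out, or for about 15 to 32 at the drop-out of the trials it cites. Where the end does exist, it is at least 16 days short of Section 6.1. The counts assume that all 150 are treated and that lacking a second biopsy means having no V7. They are counts of subjects, not of missed events.

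Four stronger readings are tempting, and the protocol does not support them:

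- **Early leavers have no post-treatment collection at all.** Section 7.8 does not place the last visit on the day of last dose, and AEs up to that visit are collected. An undefined end is not a window of zero length.
- **No early leaver ever has V7.** A subject who agrees to the second bronchoscopy may have a safety visit under Section 9.1.15.
- **The treatment-emergent window depends on completion.** The protocol does not define that window; further AE analysis details are left to the SAP.
- **Events are under-counted more on roflumilast.** An AE is a listed reason for stopping (Section 7.8), and Section 4.2 describes adverse effects associated with the drug, so a difference is possible. The protocol gives neither drop-out by arm nor event rates after stopping, so its direction and size cannot be established.

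**What to change.** Reconcile the synopsis and Sections 6.1, 9.1.15, 9.3.5, 9.3.6, 10.2.1.1, 10.2.2 and Appendix A so that they state one end of AE and SAE collection, the same number of days after last dose for every treated subject. The sponsor should choose the number. Counting from last dose is already done in this protocol for pregnancy reporting (Section 9.1.11).

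In addition:

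- Schedule the telephone contact after early withdrawal, in the text and as a row of Appendix A, for subjects without V7. Section 7.8 bars further data collection once consent is withdrawn, so the call cannot apply to those subjects; say so.
- State whether a subject who stops early but has the second bronchoscopy has V7.
- State whether the 30 days in Section 6.1 refers to following known events, to collecting new ones, or to both. If 30 days is kept as scheduled follow-up, align the 24-week maximum, since the total becomes 26.3 weeks.

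The cost is protocol wording and one short call for each subject whose last visit falls before the end of the window. If the window outlasts V7, that includes subjects who had V7: up to 105 more at the protocol's own drop-out.

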10.2.1.2 AE Reporting

At each study visit, the investigator will assess whether any subjective AEs have occurred. A neutral question, such as “How have you been feeling since your last visit?” may be asked. Subjects may report AEs occurring at any other time during the study. Subjects experiencing a serious AE must be monitored until the symptoms subside and any clinically relevant changes in laboratory values have returned to baseline or there is a satisfactory explanation for the change.

All subjects experiencing AEs, whether considered associated with the use of the study medication or not, must be monitored until the symptoms subside and any clinically relevant changes in laboratory values have returned to baseline or until there is a satisfactory explanation for the changes observed. All AEs will be documented in the AE page of the CRF, whether or not the investigator concludes that the event is related to the drug treatment. The following information will be documented for each event:

1. Event term.
2. Start and stop date.
3. Severity.
4. Investigator’s opinion of the causal relationship between the event and administration of study medication(s) (related or not related).
5. Investigator’s opinion of the causal relationship to study procedure(s), including the details of the suspected procedure.
6. Action concerning study medication.
7. Outcome of event.
8. Seriousness.

Through this follow-up if it is determined that an AE not previously reported has been identified, normal reporting requirements should be applied.

10.2.2 Collection and Reporting of SAEs

When an SAE occurs through the AE collection period it should be reported according to the following procedure:

A Takeda SAE form must be completed, in English, and signed by the investigator immediately or within 24 hours of first onset or notification of the event. The information should be completed as fully as possible but contain, at a minimum:

- A short description of the event and the reason why the event is categorized as serious.
- Subject identification number.
- Investigator's name.
- Name of the study medication(s)
- Causality assessment.

The SAE form should be transmitted within 24 hours to the attention of the contact listed in Section 1.1.

Any SAE spontaneously reported to the investigator following the routine AE collection period should be reported to the sponsor if considered related to study participation.

10.3 Follow-up of SAEs

If information not available at the time of the first report becomes available at a later date, the investigator should complete a follow-up SAE form or provide other written documentation and fax it immediately within 24 hours of receipt. Copies of any relevant data from the hospital notes (eg, ECGs, laboratory tests, discharge summary, postmortem results) should be sent to the addressee, if requested.

All SAEs should be followed up until resolution or permanent outcome of the event. The timelines and procedure for follow-up reports are the same as those for the initial report.

10.3.1 Safety Reporting to Investigators, IRBs or IECs, and Regulatory Authorities

The sponsor will be responsible for reporting all suspected unexpected serious adverse reactions (SUSARs) and any other applicable SAEs to regulatory authorities, including the European Medicines Agency (EMA), investigators and IRBs or IECs, as applicable, in accordance with national regulations in the countries where the study is conducted. Relative to the first awareness of the event by/or further provision to the sponsor or sponsor's designee, SUSARs will be submitted to the regulatory authorities as expedited report within 7 days for fatal and life-threatening events and 15 days for other serious events, unless otherwise required by national regulations. The sponsor will also prepare an expedited report for other safety issues where these might materially alter the current benefit-risk assessment of an investigational medicinal product or that would be sufficient to consider changes in the investigational medicinal products

administration or in the overall conduct of the trial. The investigational site also will forward a copy of all expedited reports to his or her IRB or IEC in accordance with national regulations.

12.0 DATA HANDLING AND RECORDKEEPING

The full details of procedures for data handling will be documented in the Data Management Plan. AEs, medical history, and concurrent conditions will be coded using the Medical Dictionary for Regulatory Activities (MedDRA [SOC, HLGT, HLT, LL, PT, and their corresponding descriptive terms]). Drugs will be coded using the World Health Organization (WHO) Drug Dictionary.

12.1 CRFs

Completed CRFs are required for each subject who signs an informed consent.

The sponsor or its designee will supply investigative sites with paper CRFs. These forms are used to transmit the information collected in the performance of this study to the sponsor and regulatory authorities. CRFs must be completed in English. All paper CRFs must be filled out legibly in black or blue ballpoint ink (use of black ink is preferred).

After completion of the entry process, computer logic checks will be run to identify items, such as inconsistent dates, missing data, and questionable values. Queries may be issued by Takeda personnel (or designees) and will be answered by the site.

Corrections are to be made by making a single-line strikeout of the incorrect information and writing in the revisions. All corrections must be initialed and dated. Reasons for significant corrections should additionally be included.

The principal investigator must review the CRFs for completeness and accuracy and must sign and date the appropriate CRFs as indicated. Furthermore, the investigator must retain full responsibility for the accuracy and authenticity of all data entered on the CRFs.

CRFs will be reviewed for completeness and acceptability at the study site during periodic visits by study monitors. The sponsor or its designee will be permitted to review the subject's medical and hospital records pertinent to the study to ensure accuracy of the CRFs. The completed CRFs are the sole property of the sponsor and should not be made available in any form to third parties, except for authorized representatives of appropriate governmental health or regulatory authorities, without written permission of the sponsor.

